#### 2.2 Method

Patient selection:

Potential candidates for this study will have been referred for a TTE by a healthcare professional. The referrals will be reviewed and if the patient meets the initial eligibility criteria, they will be considered as part of this study. The initial eligibility criteria consist of being over the age of 50 (although patients will be age-matched across the three groups) and falling within the control (normal sinus rhythm), disease-control (controlled hypertension) or disease groups (chronic AF).

Data collection:

The images obtained from the TTE scan will be stored on the ultrasound machine as well as the picture archiving systems (PACS) on the computer. The measurements to be compared are:

- Left atrium area
- Left atrium volume
- Left atrium strain measurement and analysis using the R wave

The first two measurements are routinely performed during TTEs, but atrial strain measurements are not routinely performed. This additional measurement will not affect or delay the TTE results and report from being sent back to the referrer or delay any further correspondences with other healthcare professionals. Atrial strain measurements will be conducted using the AFI LA atrial strain tool provided by GE Healthcare. These three measurements will be compared across the three groups and tested for a statistically significant difference. Providing that there is a significant

difference, particularly between the control and disease groups, a subsequent comparison will be conducted between the three groups of AF using the existing data.

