#### 2.2.3 Study Populations, Subject Selection, Recruitment and Study Schedule

Sampling design - only patients that have been referred for a transthoracic echocardiogram will be included as part of this study. Patient referrals will be screened to assess whether the patients fit into either of the three study groups. On patient arrival, patients that are deemed to be eligible thus far will be provided with an explanation of the study, patient information documents, and written informed consent is to be invited and received. Departmental sonographers may initiate Research discussion with patient either pre-during or post-scan, prior to the CI explaining the study in full and obtaining written informed consent. Providing that the transthoracic scan images are of a good enough quality to obtain strain measurements, the patient will be included as part of the study. Recruitment options will be tailored to the participant and may be either remotely or at time of clinic visit. Once potential candidates have been screened, it is envisaged that the invitation letter, Participant Information Sheet (PIS), Informed Consent Form (ICF) and a template ICF will be posted to the participant along with their appointment letter for an echocardiogram. This will allow plenty of time for potential participants to read over the PIS. The patient then may be contacted prior to their appointment via telephone to discuss the study and participant involvement and give verbal consent. If this is not feasible, the study should be discussed with patient during their appointment visit and written consent can be obtained. If the CI is not able to discuss the study with the patient at either of these times, the patient may be telephoned following their scan to discuss and provide verbal consent.

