#### Inclusion criteria:

- Criterion 1: subjects will be included in the study if they are within one of the following groups:
  - Known to be in normal sinus rhythm, are normotensive and have no underlying health problems.
  - Known to be in normal sinus rhythm and have controlled hypertension. This must have been diagnosed by a healthcare professional and the patient should be taking appropriate antihypertensive medication.
  - Known to have chronic atrial fibrillation (persistent or permanent AF). This must have been diagnosed by a healthcare professional and the patient should be appropriately anticoagulated.
- Criterion 2: subjects should ideally be ≥ 50 years, but subjects will be age matched across all three groups.
- Criterion 3: patients should have an EF  $\ge$  50%.
- Criterion 4: good quality TTE images.
- Criterion 5: No valvular pathologies.
  - Patients with AF that have < moderate valvular pathologies may be considered (as per the British Society of Echocardiography Guidelines).

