#### Exclusion criteria:

- Criterion 1: subjects with any valvular pathologies in the control and disease-control groups.
- Criterion 2: subjects with AF that have ≥ moderate valvular pathologies (as per the British Society of Echocardiography Guidelines).
- Criterion 3: subjects with an EF < 50%.
- Criterion 4: subjects < 50 years old.
- Criterion 5: poor quality TTE images.
- Criterion 6: inability to provide informed consent.
- Criterion 7: permanent atrial / ventricular pacing.
- Criterion 8: previous cardiac surgery.
- Criterion 9: unsatisfactory tracking of the LA endocardial border.
- Criterion 10: patients unwilling to have their results potentially published

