#### 2.2.5 Power Calculation

The study aims to investigate significant differences in atrial strain values between subjects with atrial fibrillation (AF), hypertension (no AF), and healthy volunteers. To

achieve statistical power for this study, a large enough sample size must be obtained. This will be achieved via the use of power calculations utilising G\*Power 3.1 Statistical support has been provided and a sample size calculation was based on data found within the literature and involved detecting the smaller difference of left atrium contractile % between subjects with atrial fibrillation and healthy volunteers. The following criteria will be utilised: alpha level of 0.05, beta level of 15% and statistical power of 85%. Hence using this minimum value to determine our sample size (expected difference of 4.0, power = 0.85 and SD  $\pm$  7.5) and one-way ANOVA at three levels, a minimum sample size of at least 78 subjects in each group will be required for this study, total of 234 participants required. See Appendix Figures 1 & 2 for power calculation plots.

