# 3. Screening, Consent and Withdrawal

# 3.1 Screening Duties

The Chief Investigator will be responsible for screening potential participants. This will be done by reviewing both in-patient and out-patient referrals to look for patients that are in one of the following categories: normal sinus rhythm, normal sinus rhythm with controlled hypertension and chronic atrial fibrillation. Subsequently, this can be further refined by excluding patients based on age, valvular pathologies and ventricular dysfunction.

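### Age matching of the three groups is promised without a procedure, and section 2.2.6 compares the groups without adjusting for age

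*Combined protocol and SAP*

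**What the plan says.** Matching is promised twice. Section 2.2 gives the initial eligibility criterion as "being over the age of 50 (although patients will be age-matched across the three groups". Inclusion criterion 2 in section 2.2.4 says "subjects should ideally be ≥ 50 years, but subjects will be age matched across all three groups".

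The selection steps are in two places. In section 2.2.3, once the images are of "good enough quality to obtain strain measurements, the patient will be included as part of the study". In section 3.1, after referrals have been sorted into groups, "this can be further refined by excluding patients based on age, valvular pathologies and ventricular dysfunction".

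Section 2.2.6 plans an independent t-test for sinus rhythm versus AF and a one-way ANOVA across the three groups, with Mann-Whitney and Kruskal-Wallis tests where normality fails. The same tests are repeated for LA area and volume. Linear regression appears only for the early-predictor question, and no covariates are named. The chi-squared check is for categorical data such as gender; no comparison of age between groups is listed. Section 4.4 shows that age is held in the study spreadsheet.

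The age limit is worded a third way among the exclusion criteria: "Criterion 4: subjects < 50 years old".

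**The concern.** A promise of matching protects a comparison only if a step delivers it, or if the analysis deals with what matching leaves behind. Here the first is not described and the second is absent.

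The documents give reason to expect an imbalance. The Introduction states that AF prevalence rises with age. Controls must be normotensive and otherwise healthy, which may favour younger referrals, although that is an inference. The lower limit of 50 removes younger patients from every group but does nothing about, say, controls in their fifties set against AF patients in their seventies.

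If strain or LA size varies with age, the unadjusted differences would mix the age effect with the effect of rhythm or hypertension, and nothing in section 2.2.6 would detect or remove it. At stake is the interpretation of the study's main comparisons, including whether hypertensive patients lie between the other two groups.

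**Working it through.** **1. Reading check.** Sections 2.2, 2.2.3, 2.2.4, 3.1 and 2.2.6 were searched for anything that would carry out matching: individual or frequency matching, age bands, a caliper, a ratio, age quotas, or a rule for an eligible patient without a match. None is there. Section 2.2.6 contains no matched-set analysis and no age covariate.

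**2. The plan's own sample size.** Section 2.2.5 uses "expected difference of 4.0, power = 0.85 and SD" "7.5) and one-way ANOVA at three levels", with alpha 0.05. Equally spaced means 0, 2, 4 have standard deviation √(8/3) = 1.633, so f = 1.633 / 7.5 = 0.2177, as in the G*Power output in the Appendix. With N = 234, λ = 234 × 0.2177² = 11.09, critical F = 3.035 and power = 0.851. The figure of 78 per group reproduces exactly. It contains no term for matching or age, so no arithmetic error arises here.

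**3. Illustration of bias from an unadjusted age difference.** The age gap and the strain-age slope are assumptions; neither is in the documents.

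- Bias = slope × age gap.
- SE of the difference at 78 per group = 7.5 × √(2/78) = 1.201.
- Rejection rate with no true rhythm effect: two-sided noncentral t, 154 df, noncentrality = bias / 1.201.

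| Assumed slope (points/year) | Assumed age gap (years) | Bias (points) | Share of 4.0 | Rejection rate (nominal 5%) |
|---|---|---|---|---|
| 0.1 | 5 | 0.5 | 13% | 7.0% |
| 0.15 | 8 | 1.2 | 30% | 16.8% |
| 0.2 | 10 | 2.0 | 50% | 38.0% |
| 0.3 | 10 | 3.0 | 75% | 69.9% |

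Wider assumptions (up to 0.4 per year and 15 years) take the bias to 6.0 points, 150% of the planned difference. The spread reflects the inputs chosen.

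**4. Cost of adjusting, sinus rhythm versus AF contrast of 4.0.** Also assumed: age SD of 8 to 10 years within groups, and slope 0.1 to 0.3.

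- Variance inflation v = 1 + [gap² / (3 × 77 × SD_age²)] / (2/78).
- Share of strain variance explained by age, r² = (slope × SD_age / 7.5)².
- SE = 7.5 × √[(1 − r²) × v × 2/78]; power = Φ(4/SE − 1.96).

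Example: gap 10, age SD 8, slope 0.2. v = 1 + (100/14,784)/(2/78) = 1.264; r² = 0.046; SE = 1.319; power = Φ(3.03 − 1.96) = 0.858.

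| Age gap (years) | v | Power, range over assumptions |
|---|---|---|
| 0 | 1.00 | 92% to 95% |
| 5 | 1.04 to 1.07 | 90% to 95% |
| 10 | 1.17 to 1.26 | 85% to 92% |
| 15 | 1.38 to 1.59 | 76% to 87% |

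**The case against.** The strongest defence is that matching is itself part of inclusion criterion 2, that one person screens all referrals, and that section 3.1 lets that person exclude on age without naming a cut-off. Excluding on age at referral is one way to frequency-match. The inclusion sentence in section 2.2.3 is an image-quality condition for patients already judged eligible so far, and it does not override criterion 2. This stands. A reader might infer that enrolment cannot produce matched groups, or that the study is bound to be reported as matched when it is not. The documents support neither; they show only that the method is unstated.

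A reader might also infer that the bias must favour the study's hypothesis. That requires strain to fall, or LA size to rise, with age. The documents link age to AF prevalence and say nothing on either.

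The rejection rates suppose no true difference between sinus rhythm and AF, whereas the protocol expects one, with contractile strain absent in AF. The 4.0 and SD 7.5 themselves come from contractile strain, which section 1.1 says may not be analysable. So the rates are not a forecast. Confounding probably matters more for the hypertension contrast and for the size of the estimated effects.

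Finally, the conflicting age wording might suggest that patients under 50 could enter. Inclusion and exclusion criteria apply together, so exclusion criterion 4 bars them. What remains is the contradiction between a preference and an absolute limit, and the status of a patient aged exactly 50.

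None of this answers the analysis point: even careful matching can leave a residual difference, and section 2.2.6 does not adjust for it.

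**Conclusion.** The concern holds in this form: matching is promised without a procedure, and the planned comparisons do not adjust for age, so any residual age difference would be attributed to rhythm or hypertension. This rests on reading alone. That imbalance is plausible follows from the protocol's own statement about AF and age. How large it would be, and which way it would move strain, cannot be derived from the documents; the 0.5 to 3.0 points and the 7% to 70% are illustrations under stated assumptions. The sample size of 234 is reproduced and is not in question here. The age-limit wording is a minor, near-editorial matter.

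**What to change.** In section 2.2.6, pre-specify age as a covariate in the sinus rhythm versus AF comparison and in the three-group comparison, for strain, LA area and LA volume, using a linear model (ANCOVA). Where normality fails, use a transformed outcome or a rank-based ANCOVA in place of the unadjusted Mann-Whitney or Kruskal-Wallis test. Report the age distribution by group.

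Describe the study as age-matched only if a matching step was actually applied at screening, and in that case say what it was. Otherwise remove the wording from sections 2.2 and 2.2.4. Age quotas set by the AF group would be hard to run, because all groups are recruited at the same time over five months and the older control bands may not fill. The roughly 1200 scans in section 2.2.2 are all scans, not eligible patients.

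Reconcile the three statements of the age limit in section 2.2, inclusion criterion 2 and exclusion criterion 4; which one applies is for the sponsor to decide.

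The cost is amendment wording and one covariate already collected. The downside is some loss of precision if ages differ widely: under the assumptions above, power for a 4.0-point contrast stays at about 85% or more up to a 10-year gap and may fall to about 76% at 15 years. With little overlap in age, the adjusted result would also lean on the assumed straight-line age effect, which is a further reason to report age by group.

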#### Exclusion criteria:

- Criterion 1: subjects with any valvular pathologies in the control and disease-control groups.
- Criterion 2: subjects with AF that have ≥ moderate valvular pathologies (as per the British Society of Echocardiography Guidelines).
- Criterion 3: subjects with an EF < 50%.
- Criterion 4: subjects < 50 years old.
- Criterion 5: poor quality TTE images.
- Criterion 6: inability to provide informed consent.
- Criterion 7: permanent atrial / ventricular pacing.
- Criterion 8: previous cardiac surgery.
- Criterion 9: unsatisfactory tracking of the LA endocardial border.
- Criterion 10: patients unwilling to have their results potentially published

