The correlation between AF and a dilated LA are widely recognised, however, LA enlargement may be both a cause and consequence of AF. Dilation of the LA has been largely suggested to be due to atrial remodelling as a result of a change in atrial function and structure – as seen in the case of AF. However, there are other factors which affect atrial function and structure which ultimately result in atrial remodelling. This includes pathologies such as mitral valve disease (mitral stenosis, regurgitation, or a mixed disease), structural cardiac disease (such as heart failure, cardiomyopathies, and congenital disease) and hypertension (Van De Vegte, *et al.*, 2021). As hypertension can also cause atrial remodelling and is a risk factor for AF, patients that are in normal sinus rhythm (NSR) that have controlled hypertension are included in this study as a disease-control group. It is expected that the atrial strain values of these patients will fall between those of the control group (NSR) and of those in the disease group (chronic AF).

Existing available literature (see document Literature Review Table) suggests that there is a significant difference in the strain values between patients in NSR to those in AF. However, limited studies have included hypertensive patients or investigated

the differences in strain values between AF patients. Furthermore, previous studies have been limited by method technique. This is because many studies have either used external STE software to create atrial strain values or have adopted global longitudinal strain (GLS) methods to track the LA. This is a significant limiting factor as GLS methods are intended to assess longitudinal function of the left ventricle.

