# 1.1 Background

From the current literature available (*see document Literature Review Table*), it has been suggested that there is a correlation between AF and LA strain values. Existing literature suggests that patients in AF have a reduced LA strain value compared to patients in NSR. However, there are limited studies which also include controlled hypertensive patients despite collecting data regarding blood pressure. Furthermore, the majority of literature reviewed appears to focus on patients that have other comorbidities, and it could be argued that these can affect the parameters measured and analysed. This includes studies involving patients with valvular pathologies such as aortic stenosis and aortic valve replacements as well as studies involving patients with potential structural heart deformations such as those seen with heart failure or following a myocardial infarction. These factors may alter strain patterns and LA size as a result. By listing these factors as exclusion criteria, this study should minimise any external and uncontrollable factors which may affect LA strain value and LA size.

Furthermore, some studies do not have a standardised zero-reference point as some studies used the P wave for NSR and the R wave for AF patients which may cause a discrepancy in results. In this study, it has been agreed that the zero-reference point will be the R wave to create R-R cycles. This is because the P wave is not present in AF and thus cannot be used as a definitive reference point within the AF group. Both groups will have R waves present and therefore, the reference-point can be standardised across all three groups. Additionally, many of the studies reviewed appear to focus on only one LA strain and phase within the cardiac cycle. However, some do include all three. This study will include all three strain values as well as peak atrial longitudinal strain (PALS) values. However, statistical analysis may not be doable for the contractile phase as this is not present in patients with AF. The biggest pitfall that is common to most, if not all, studies reviewed is that the methods used to calculate LA strain were originally designed to measure global longitudinal strain (GLS) of the left ventricle (LV). This study utilises the automated function imaging (AFI) LA atrial strain tool provided by GE Healthcare which is specific to the LA as opposed to GLS methods to track the LV.

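### Section 1.1 says heart failure and previous infarction are listed as exclusions, but 2.2.4 lists neither and allows mild valve disease in the AF group only, so an NSR-AF difference cannot be credited wholly to AF.

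*Combined protocol and SAP*

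**What the plan says.** Section 1.1 (Background) argues that earlier studies were weakened by comorbidity. It names valve pathologies and "potential structural heart deformations such as those seen with heart failure or following a myocardial infarction", says these may change strain and LA size, and concludes: "By listing these factors as exclusion criteria, this study should minimise any external and uncontrollable factors which may affect LA strain value and LA size".

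The Introduction (Section 1) lists conditions other than AF that remodel the atrium: mitral valve disease, "structural cardiac disease (such as heart failure, cardiomyopathies, and congenital disease) and hypertension".

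Section 2.2.4 then sets the criteria:

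- **All groups:** EF of at least 50% and no previous cardiac surgery. Neither heart failure nor myocardial infarction appears in the inclusion or exclusion list.
- **NSR controls only:** normotensive and otherwise healthy. The hypertensive and AF groups have no such condition.
- **Valve disease:** the exclusions remove "subjects with any valvular pathologies in the control and disease-control groups". For the AF group, the inclusion list says: "Patients with AF that have < moderate valvular pathologies may be considered".

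Section 3.1 adds screening on age, valve pathology and ventricular dysfunction, without defining the last. Section 2.2.6 compares the groups by t-test, one-way ANOVA or their rank equivalents, for strain and again for LA area and volume. It names no covariate and no sensitivity analysis for structural or valve disease.

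**The concern.** The protocol identifies certain diseases as disturbing the measurements, presents their exclusion as an advantage over earlier work, and then does not write two of them into the criteria. The omission is not neutral between groups. The control group has a general health requirement that keeps these diseases out; the AF group does not. The valve rule is also stricter for controls than for AF patients.

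The main contrast is NSR against AF. If the AF group carries other causes of atrial remodelling and the control group carries none, part of any difference in strain or LA size may come from those causes. The hypertensive group cannot separate out the valve effect, because it too must be free of valve lesions. The comparison of AF subtypes goes ahead only if the first comparison is significant (2.1 and 2.2), so the same imbalance affects whether it is run.

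**Working it through.** **1. Claim against criteria.**

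| Factor named in 1.1 | NSR controls | Hypertensive group | AF group |
|---|---|---|---|
| Heart failure, EF below 50% | excluded | excluded | excluded |
| Heart failure, EF 50% or more | kept out by the general health requirement | eligible | eligible |
| Previous infarction, EF below 50% or cardiac surgery | excluded | excluded | excluded |
| Previous infarction, EF 50% or more, no surgery | kept out by the general health requirement | eligible | eligible |
| Valve disease, moderate or worse | excluded | excluded | excluded |
| Valve disease, less than moderate | excluded | excluded | may be considered |

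Three rows differ between NSR and AF, each time with the AF group the more permissive. Only the last row also separates the hypertensive group from AF.

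**2. Does the screening step close the gap?** Section 3.1 mentions ventricular dysfunction, but the only ventricular threshold in 2.2.4 is EF of 50%. Read with that threshold, screening removes no one whom the EF criterion would keep.

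**3. Does the analysis repair it?** No adjustment is planned in 2.2.6. The data items in 2.2.2 are demographics, heart rate and rhythm, LA area and volume, and strain. Section 4.4 adds referral reason and ends its list openly. Neither names comorbidity or valve grade, so a later check is not assured.

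**4. Form of the bias.** Let a share p of the AF group have such a condition, let it lower strain by d points on average, and let the share among NSR controls be zero. Then:

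observed difference = difference due to AF + p × d

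The documents give neither p nor d. With assumed values:

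- p = 10%, d = 1: 0.10 × 1 = 0.1 points
- p = 25%, d = 2: 0.25 × 2 = 0.5 points
- p = 50%, d = 4: 0.50 × 4 = 2.0 points

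For hypertension against AF, the heart failure and infarction part is (p in AF − p in hypertension) × d, which could have either sign. The valve part remains p × d.

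**5. Why these are not scaled to the planned difference.** The sample size reproduces. Evenly spaced means 0, 2, 4 with SD 7.5 give f = 0.2177; then λ = 234 × 0.2177324² = 11.093, and power is 0.851 at N = 234. But Section 2.2.5 states that the 4.0 is a difference in contractile strain. The Introduction expects that phase to be missing in AF, and 1.1 says it may not be analysable. The bias would act on reservoir and conduit strain and on LA size, for which the plan gives no expected difference or SD. A percentage of 4.0, or a false-positive rate using SD 7.5, would therefore have no proper basis.

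**The case against.** **The existing criteria already cover much of this.** The EF limit, the surgery exclusion and the ventricular dysfunction screen remove many patients with heart failure or infarction, and 1.1 promises only to minimise such factors. This stands as far as it goes: a reader might infer that these diseases are not screened for at all, and that would be wrong. The gap is limited to patients with EF of 50% or more and no surgery. It remains a gap, because 1.1 says the factors are listed, and two are not.

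**The valve rule is deliberate.** It appears in both lists, is capped below moderate and is tied to a named grading guideline. A reader might infer that the criteria contradict each other; they do not. The conflict is with the rationale in 1.1. The protocol also says that causes of AF can be its by-products. If some mild lesions follow from AF, removing those patients could leave an unrepresentative AF group. This stands, and is a reason to treat valve disease by sensitivity analysis.

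**Cardiomyopathy and congenital disease.** A reader might add these to the broken promise. They appear in the Introduction as causes of remodelling, not in 1.1, and the plan nowhere says they are excluded.

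**A single less-than-moderate valve limit for all groups** looks like a simple remedy. It would move the study further from 1.1 and sit badly with the requirement that controls be otherwise healthy. It would equalise the threshold, not the frequency of lesions.

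**Conclusion.** The mismatch between 1.1 and 2.2.4 is certain for heart failure and previous infarction with EF of 50% or more. The AF-only valve allowance is a stated design choice that departs from the rationale in 1.1. Because the comparisons are unadjusted, an NSR-AF difference in strain or LA size cannot be credited wholly to AF.

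The size of the bias is unknown. The 0.1 to 2.0 points above rest entirely on assumed shares and effects, and on no such disease among controls. The direction, towards exaggerating the AF difference, assumes that these conditions lower strain and enlarge the atrium, as the Introduction and 1.1 imply. For valve disease it also assumes that the lesions are not themselves a result of AF.

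A reader might go further and infer that a positive result would say nothing about AF. The documents do not support that: they give no frequency or effect from which the bias could be shown to account for the whole difference.

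**What to change.** 1. **Reconcile 2.2.4 with 1.1.** List known heart failure, whatever the EF, and previous myocardial infarction as exclusions for all groups. If the sponsor prefers to keep these patients, remove the claim in 1.1 that the factors are listed as exclusions.
2. **Record valve grade** for every participant from the echocardiogram already performed, and name it among the data items in 2.2.2.
3. **Pre-specify one sensitivity analysis in 2.2.6:** repeat the NSR-AF and three-group comparisons, for strain and for LA area and volume, without AF participants who have any valve lesion. State beforehand that some mild lesions may result from AF, so a smaller difference in this analysis would not by itself show confounding.

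The cost is a change of wording, one extra data item and one extra analysis; no additional visit is needed. Somewhat fewer AF and hypertensive patients will be eligible. The documents give no breakdown of referrals from which to say how many. The sensitivity analysis also has a smaller AF group. If 25% of the planned 78 had a lesion, about 58 would remain (78 × 0.75 = 58.5); if 50%, 39 (78 × 0.50). Both shares are assumptions. It should therefore be judged by its estimate and confidence interval, not by whether significance is retained.
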